12.3 Analysis Populations

- The intent-to-treat (ITT) population will include all patients randomized to a treatment group who are randomized and receive at least one dose of the study drug. The ITT population will be used for the primary analyses of all study endpoints, taking into consideration the specific populations described below. The patients will be kept in their randomized treatment arm for the analyses.
- The per-protocol (PP) population will include all patients randomized to a treatment group to whom at least 12 days of study treatment are administered in accordance with the protocol (i.e. without major protocol deviations as pre-identified prior to the database lock) and without interruption triggering withdrawal from further treatment (see Section 8.3). The PP population will serve as the basis for secondary analyses of all study endpoints. The patients will be kept in the treatment arm that they actually received for the analyses.
- The safety population will include all patients randomized to a treatment group who received at least one dose of study drug treatment. This population will serve as the basis for analyses of all safety endpoints. The patients will be kept in the treatment arm that they actually received for the analyses.

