8.3 Study Drug Discontinuation and Withdrawal of Patients

Patients should discontinue permanently the study drug in the event of any of the following (Since a low LAU-7b dose is used in this study, no dose reductions are planned):

- 1. If a patient is escalated to invasive mechanical ventilation preventing the administration of the study medication intact;
- 2. Occurrence of a SAE deemed related to the study drug that is a life-threatening adverse reaction or one resulting in prolonged non-COVID-19 disease-related hospitalization;

LAU-7b for the treatment of COVID-19 disease in Adults

² When a factor that may potentially affect renal function by hemodynamic mechanisms is known or suspected on admission (Ex: dehydration), it is recommended to rule out a possible renal impairment by addressing the issue whenever possible (Ex: rehydration) and reassessing CrCL prior to signing the ICF.

- 3. If the patient, Investigator, or Laurent determines that it is not in the best interest of the patient to continue treatment;
- 4. If a patient is serially and persistently noncompliant with study procedures and/or assessments, the investigator or the sponsor may withdraw the patient from further treatment;
- 5. A patient's treatment is unblinded by the Investigator;
- 6. If a female patient has a confirmed pregnancy (with the exception of a pregnancy resulting from *in-vitro* fertilization), this should be immediately reported to the Medical Monitor and Laurent Pharmaceuticals (within 24 hours awareness) and the patient shall discontinue the study drug. Pregnancy, whether in a patient or in a partner of a patient should be followed up until conclusion, with an assessment of child health at birth:
- 7. Considering the safety observed so far in the study, patients showing possible kidney impairment as depicted by either:
 - a. An increase from screening in serum creatinine of 0.5 mg/dL or 2x the screening value if the serum creatinine was within normal range at screening and the calculated CrCL was \geq 30 ml/min;
 - b. An increase of serum creatinine $\geq 2x$ the screening value if the screening value was above the normal range and the calculated CrCL was ≥ 30 ml/min.
- 8. Notwithstanding that the study so far confirms the lack of a particular drug-related liver toxicity, patients showing possible liver impairment as assessed with the liver safety algorithm based on the Drug Induced Liver Injury (DILI) algorithm, described in Section 11.4

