- 9. As soon as the site is informed, patients missing two consecutive doses or more than two non-consecutive doses at any point during the treatment period.

Patients withdrawn from further treatment but agreeable to provide outcome information should continue to undergo the safety and efficacy assessments as per protocol, whenever possible, up to Day 60. In all cases, the reason for study drug discontinuation will be noted on the CRF. This is in the view of maximizing the number of patients with actual follow-up information and minimizing patients lost to follow-up.

Patients should be withdrawn from the study in the event of any of the following:

- 1. If the patient withdraws consent to participate in the study as a whole;
- 2. If the patient is lost to follow-up.

The patient has the right to withdraw from the study at any time. Nevertheless, investigators will be trained to minimize full withdrawals from study wherever possible. Survival status and the requirement for invasive mechanical ventilation up to Day 60 are absolutely necessary for all randomized participants and should still be reported for participants who withdraw from the study, where permitted by local guidelines. Site staff should make multiple attempts to contact patients who miss a study visit; it is better to have a late visit than a missed visit.

The reason for patient withdrawal from the study will be noted on the CRF. Where applicable, the investigator should attempt to follow patients withdrawn from study until resolution of any adverse events. Upon withdrawal, no further dosing should be performed for these patients. Investigators shall make reasonable attempts to contact lost-to-follow-up patients for evaluation.

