9.3 Study Drug Treatment

The total duration of study treatment is up to 14 consecutive days of either LAU-7b or placebo, as follows:

Eligible patients will be randomized (1:1) to receive in a blinded fashion, either LAU-7b 300 mg per day (3 capsules of 100 mg each), once a day for 3 days, or a matching placebo administered in the same fashion (the "Initial Treatment").

From Day 4, patients will continue the treatment with LAU-7b 200 mg per day (2 capsules of 100 mg each), once a day for the remaining 11 days, or a matching placebo administered in the same fashion (the "Follow-up Treatment").

All eligible and confirmed patients will be treated and closely monitored for a period of up to 2 weeks or until early termination. The last day of study drug treatment will be on Day 14 or earlier due to aggravation preventing oral intake of study medication or death, whichever comes first. Specifically, patients undergoing intubation preventing oral intake of study medication will not receive the drug by other means such as through a feeding tube. Patients will continue their study participation as planned except for procedures that cannot be performed due to disease aggravation.

In all cases, the study treatment will be administered on top of current SOC therapies for COVID-19 disease.

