12 STATISTICAL ANALYSIS

A statistical analysis plan (SAP) will provide details of the methods of analysis to address all study objectives. The SAP may be amended during the course of the study, but will be finalized before the cutoff date for any analysis, interim or final.

Data summaries by treatment group will be presented. For categorical data such as the 7-point Ordinal Scale, data will be tabulated in frequency tables to display the number and proportion of patients for each category by treatment group. For continuous variables, data will be summarized with the number of patients, mean, standard deviation, median, and minimum and maximum values by treatment group. Baseline assessments for each outcome variable will be defined as the screening measurement unless a repeat value was obtained, see restrictions in Section 9.2.1.1, before the first dose of study drug. Statistical significance will be set at the 5% level (one-sided) for the pilot portion and at the 5% level (two-sided) for the extension. Consideration

will be given for adjusting for pre-specified prognostic baseline factors such as age, the ordinal scale health status at baseline and comorbidities, where applicable.

Diligent efforts will be made to prevent missing data in the study. For example, patients who discontinue the study treatment early should still be followed for all regularly scheduled visits for safety and relevant efficacy assessments, until the Day 60 follow-up. A clear distinction should be made between treatment discontinuation and study withdrawal. Efficacy assessments occurring after treatment discontinuation should not be included in the per-protocol analysis.

Database lock and statistical analyses will be performed for the pilot portion and the extension, separately.

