12.4 Estimand Strategy

Some types of intercurrent events are expected to possibly occur during the course of the study: treatment interruption; treatment discontinuation; and use of disallowed medication (see Section 9.5.1). The project estimands strategies, including those for handling each of these types of intercurrent events are summarized in Table 3 below.

Table 3: Primary Objective and Estimands with Rationale for Strategies to Address Intercurrent Events in Phase III

Objective: To evaluate the efficacy of LAU-7b therapy + Standard-of-Care (SOC) relative to placebo + SOC in patients with COVID-19 disease with confirmed SARS-CoV-2 infection.			
Target Population	Adult subjects with COVID-19 disease with confirmed SARS-CoV-2 infection and a Health Status score 3 or 4 at baseline.		
Variable/Endpoint	The 7-point ordinal scale of the patient status / The proportion of patients requiring mechanical ventilation AND/OR deceased (all causes) by Day 60		
Primary Estimand			
Intercurrent events 1.Treatment Interruption 2.Treatment Discontinuation for Other Reasons than death 3.Use of Disallowed Medication	Treatment Policy strategy	1. For temporary interruptions of study treatment (e.g. due to an adverse event), data collected will be analyzed as if treatment had continued normally throughout the study. If the treatment is interrupted and then never restarted (e.g. due to subject death, withdrawal) then it will be treated as per treatment discontinuation strategies below. 2. For endpoints where the subject has data available, the subject will continue to be analyzed as part of their treatment group even if they have discontinued treatment. Missing data are not considered part of this intercurrent event and are handled separately (see the appropriate Section 12.7 or 12.8 for handling depending upon endpoint). 3. If a subject is given disallowed medication (see Section 9.5.1) after enrollment, their safety and efficacy data will be analyzed as normal.	
Intercurrent events 4. Treatment Discontinuation due to Lack of Efficacy (mechanical ventilation) or Safety Event (death)	Composite event strategy	4. Serious safety events and/or indications of lack of efficacy (e.g. death, mechanical ventilation) are included in study endpoints as part of analyses. Therefore, treatment discontinuation due to most anticipated types of safety/lack of efficacy events are accounted for in the endpoints and analyses	

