Population-Level Summary	The proportion of patients requiring mechanical ventilation (includes ECMO) AND/OR deceased by Day 60 will be analyzed using a Fisher		

	exact test to compare proportion of LAU-7b treated subjects relative to placebo.
Estimand Description	Superiority of LAU-7b on the proportion of patients requiring mechanical ventilation or deceased by Day 60 will be analyzed using Fisher exact test irrespectively from the interruption of treatment, early discontinuation of the treatment (for other reason than death) or use of disallowed medication.
Imputation/Data/Censoring Rule(s)	Missing observations will be treated as a non-response (i.e. patient considered as Health Status 6-7 inclusively) for the primary analyses on ITT.
Sensitivity Analysis	Sensitivity analyses where missing observations will be imputed using different methods will also be performed and will be further detailed in the SAP.

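### Per-protocol membership depends partly on the primary outcome: ventilation that stops oral dosing, or death, before the 12th dosing day removes a patient who had complied until then

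*Protocol*

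**What the plan says.** Protocol Section 12.3 sets two exposure conditions for PP: "at least 12 days of study treatment are administered in accordance with the protocol", and no interruption that triggers withdrawal from treatment under Section 8.3. It also gives PP a broad role: "The PP population will serve as the basis for secondary analyses of all study endpoints".

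Dosing is planned for 14 days. The first reason for permanent discontinuation in Section 8.3 is "If a patient is escalated to invasive mechanical ventilation preventing the administration of the study medication intact". The ninth concerns "patients missing two consecutive doses or more than two non-consecutive doses at any point during the treatment period". Section 9.3 puts the last dosing day at Day 14 or "earlier due to aggravation preventing oral intake of study medication or death", and rules out feeding-tube administration after intubation.

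The primary endpoint (Section 7.1.2) is mechanical ventilation and/or death by Day 60. For the primary estimand, Section 12.4 uses a composite strategy: "Serious safety events and/or indications of lack of efficacy (e.g. death, mechanical ventilation) are included in study endpoints as part of analyses". The missing-data rule in the same table is stated "for the primary analyses on ITT".

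The opening text of Section 12 adds a data rule for PP: "Efficacy assessments occurring after treatment discontinuation should not be included in the per-protocol analysis".

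The SAP Addendum leaves the sensitivity and supplementary analyses unchanged and lists a PP table (14.2.3.2.1e) for the Day 29 endpoint.

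**The concern.** A per-protocol set is meant to select on adherence. Here the exposure threshold also selects on the outcome. Consider two patients who take every dose offered. One has no event and completes 14 days. The other is intubated on Day 6 and cannot swallow capsules. The first is in PP and the second is not, although neither departed from the protocol.

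Readers usually take agreement between PP and ITT as reassurance and disagreement as a warning. On an endpoint made of the events that cause exclusion, neither reading is safe. A drug whose benefit is preventing early ventilation could show almost nothing in PP. Equally, an ineffective drug could look better or worse in PP if the timing of events differed between arms.

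**Working it through.** **The rules side by side.** Section 12.3 needs 12 dosing days. Sections 8.3 (first item) and 9.3 end dosing at ventilation that prevents oral intake, or at death. Section 7.1.2 counts both as primary events. No exemption for a patient who complied until the event appears in the protocol or the SAP Addendum. A patient who completes the 14 days and has an event later does meet the definition, so only part of the events is affected.

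**The plan's own figures.** Section 5.4.2.1 reports, for pilot patients with baseline status 3 or 4, 0/76 on LAU-7b and 5/72 (6.9%) on placebo progressing to ventilation, p=0.025. The two-sided Fisher exact test gives 0.0253, so this reproduces. Section 12.1 plans for 7% versus 0% with 132 per arm and at least 90% power. Exact Fisher power at 132 per arm is 90.6%, so this reproduces too, and it does not involve PP.

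**Notation.** p is the true event rate and s the share of events before the 12th dosing day. The documents do not give s, so every value below is an assumption. Other PP exclusions are assumed to fall equally on event and event-free patients within an arm, so they cancel.

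*Event rate in PP* = p(1−s) / (1−ps). With p = 0.07:
- s = 0.25: 0.0525/0.9825 = 5.3%
- s = 0.50: 0.035/0.965 = 3.6%

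*Odds ratio in PP* = true odds ratio × (1−s_active)/(1−s_placebo).

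- Drug prevents only early events: placebo 7% with half early, active 3.5% with all late.
  - ITT: (0.035/0.965)/(0.07/0.93) = 0.48
  - PP: (0.035/0.965)/(0.035/0.93) = 0.96
- No true effect, early shares of 80% active and 40% placebo: 0.2/0.6 = 0.33. With the shares reversed: 0.6/0.2 = 3.0. These shares have no anchor in the documents. They show that the bias can go either way, not how large it is likely to be.

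*Sensitivity to a single exclusion.* If one of the five pilot placebo events had been early, and there were no other PP exclusions, 0/76 versus 5/72 would become 0/76 versus 4/71. The Fisher p-value moves from 0.025 to 0.052.

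**Day 29 endpoint.** The same patients are removed, but the direction is again open. Protocol Section 7.1.3 words the endpoint as by Day 29, and the Addendum table title as on Day 29. Under the second wording, a patient ventilated early who has recovered counts as a success.

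**The Section 12 data rule.** It might also remove the event of a patient who stays in PP. This is uncertain. Under Sections 7.1.1 and 10.1 the worst status of a day is recorded as that day's score. A first score of 6 therefore belongs to the day ventilation starts, which is not clearly after discontinuation.

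**The case against.** The case for leaving the plan alone is that PP is secondary. No decision rule, alpha allocation or sample-size step uses it, and the primary analysis on ITT counts ventilation and death as outcomes. Selection of this kind is a familiar limit of exposure-based PP sets, and one sentence in the CSR might be enough. The illustrations rest on assumed timing. Protocol Section 12.7.1 defers full details to the SAP, and the main SAP was not available. Any new analysis would also follow the release of results on 14MAR2024.

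Most of this stands and limits the point, but does not remove it. Section 12.3 gives PP a role for all study endpoints, and the text available contains no exemption.

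Stronger readings are tempting and are not supported:

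- A reader might infer that the PP rule contradicts the composite estimand. Section 12.4 concerns the primary analysis on ITT, so the two target different quantities. This is a mismatch, not a contradiction.
- A reader might infer that PP must understate the event rate or the benefit. The direction depends on the early share in each arm and on other exclusions, none of which is reported.
- The pilot PP set kept 132 of 232 patients (56.9%, Section 5.4.2.1). That might suggest heavy loss through events, but the figure covers all baseline statuses, including 84 patients with status 5, and the reasons for exclusion are not given.

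**Conclusion.** The point holds for the secondary PP analyses of the ventilation/death endpoint and the related Day 29 endpoint. As written, the rule excludes compliant patients because they had an early primary event, so these results are conditional on avoiding such events and cannot serve as independent support for ITT.

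The size is unknown. Under the stated assumptions a 7% rate becomes 5.3% or 3.6%, a true odds ratio of 0.48 can appear as 0.96, and one reclassified pilot patient moves p across 0.05. The conclusion rests on the protocol text and would change if the SAP of 29SEP2023 already keeps such patients in PP. Confidence is medium for that reason. The ITT primary analysis and N=264 are not touched. This should be addressed, but it does not threaten the primary result.

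**What to change.** If the main SAP already handles these patients, cite that section and close the point. Otherwise:

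1. Beside the original PP tables (including 14.2.3.2.1e), add a supplementary PP analysis labelled post-hoc. Assess adherence only up to the date of first ventilation/ECMO or death, using recorded dates.
2. Keep the patient in PP, and count the event, if none of the following came before that date: a pre-identified major deviation, the missed-dose trigger in Section 8.3 (ninth item), or study-drug discontinuation for any other Section 8.3 reason. Do not drop the event under the Section 12 data rule.
3. State in the CSR that the original PP results on these endpoints are conditional on avoiding early events and are descriptive only.

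Two downsides must be stated with the supplement. Event patients qualify with fewer doses than event-free patients, in the extreme after a single dose. The supplement therefore also depends on the outcome and is supportive only. Patients whose dosing stopped for aggravation preventing oral intake before ventilation (Section 9.3) may still be excluded, so their number should be reported by arm.

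The cost is one derivation from existing dates, a small set of tables and one CSR statement. No new data are needed, no dosing rule changes, and the original PP tables and the ITT analysis stay as they are.

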12.4 Estimand Strategy

Some types of intercurrent events are expected to possibly occur during the course of the study: treatment interruption; treatment discontinuation; and use of disallowed medication (see Section 9.5.1). The project estimands strategies, including those for handling each of these types of intercurrent events are summarized in Table 3 below.

Table 3: Primary Objective and Estimands with Rationale for Strategies to Address Intercurrent Events in Phase III

Objective: To evaluate the efficacy of LAU-7b therapy + Standard-of-Care (SOC) relative to placebo + SOC in patients with COVID-19 disease with confirmed SARS-CoV-2 infection.			
Target Population	Adult subjects with COVID-19 disease with confirmed SARS-CoV-2 infection and a Health Status score 3 or 4 at baseline.		
Variable/Endpoint	The 7-point ordinal scale of the patient status / The proportion of patients requiring mechanical ventilation AND/OR deceased (all causes) by Day 60		
Primary Estimand			
Intercurrent events 1.Treatment Interruption 2.Treatment Discontinuation for Other Reasons than death 3.Use of Disallowed Medication	Treatment Policy strategy	1. For temporary interruptions of study treatment (e.g. due to an adverse event), data collected will be analyzed as if treatment had continued normally throughout the study. If the treatment is interrupted and then never restarted (e.g. due to subject death, withdrawal) then it will be treated as per treatment discontinuation strategies below. 2. For endpoints where the subject has data available, the subject will continue to be analyzed as part of their treatment group even if they have discontinued treatment. Missing data are not considered part of this intercurrent event and are handled separately (see the appropriate Section 12.7 or 12.8 for handling depending upon endpoint). 3. If a subject is given disallowed medication (see Section 9.5.1) after enrollment, their safety and efficacy data will be analyzed as normal.	
Intercurrent events 4. Treatment Discontinuation due to Lack of Efficacy (mechanical ventilation) or Safety Event (death)	Composite event strategy	4. Serious safety events and/or indications of lack of efficacy (e.g. death, mechanical ventilation) are included in study endpoints as part of analyses. Therefore, treatment discontinuation due to most anticipated types of safety/lack of efficacy events are accounted for in the endpoints and analyses	
Population-Level Summary	The proportion of patients requiring mechanical ventilation (includes ECMO) AND/OR deceased by Day 60 will be analyzed using a Fisher		

	exact test to compare proportion of LAU-7b treated subjects relative to placebo.
Estimand Description	Superiority of LAU-7b on the proportion of patients requiring mechanical ventilation or deceased by Day 60 will be analyzed using Fisher exact test irrespectively from the interruption of treatment, early discontinuation of the treatment (for other reason than death) or use of disallowed medication.
Imputation/Data/Censoring Rule(s)	Missing observations will be treated as a non-response (i.e. patient considered as Health Status 6-7 inclusively) for the primary analyses on ITT.
Sensitivity Analysis	Sensitivity analyses where missing observations will be imputed using different methods will also be performed and will be further detailed in the SAP.

